Standard Care Arm: Patients will receive prehospital crystalloid infusion or blood component transfusion resuscitation per site standard care for the respective EMS unit/service once all inclusion criteria and no exclusion criteria are met. Once the patient arrives at a participating site and prehospital initiated standard care transfusions are completed, patients will receive standard in-hospital trauma care.

Randomization and Masking: A single stage cluster randomization scheme will be utilized. Participating EMS services/agencies at each site will follow a fixed randomization approach of (LTWB O), (LTWB O), (Standard Care), with the initial treatment being randomly assigned. Thus an EMS service/agency will be randomly assigned to one of three three-month repeated

sequences: (1) LTWB O), (LTWB O), (Standard Care); (2) LTWB O), (Standard Care), (LTWB O); and (3) (Standard Care), LTWB O), (LTWB O)

Communication with the blood bank transportation services and each respective air base or EMS unit/service will occur and an annual schedule of randomization assignment will be distributed to each study site and respective EMS base/service. This specific randomization scheme is required due to the limited supply, goal of minimization of wastage of LTWB O, and the logistics and delivery of the intervention in the prehospital setting. The proposed trial will be an open label trial as blood product transfusion requires appropriate documentation and essential look back procedures.

III. Outcomes

Primary Outcome: The primary outcome for the clinical trial will be all cause 30-day mortality.

30-day mortality will be checked by calling the participant directly with the phone number they provided. If there is no response from the patient, 30-day mortality will be checked by searching public databases such as the National Death Index.

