Inclusion and exclusion criteria will be assessed based on available information at the time of enrollment in the prehospital environment. Although all reasonable efforts will be made by the EMS crews to either directly witness or obtain documentation of eligibility criteria, due to the nature of the emergency pre-hospital setting, there may be occasions where the EMS crew must rely on verbal report of inclusion criteria, including qualifying vitals, from the referring hospital or ground crew. In these instances, if, after subsequent review of outside hospital and/or ground crew documentation, it is determined that the subject did not meet inclusion criteria and/or met exclusion criteria, the subject will remain enrolled in the study based on the intention-to-treat principle.

In the event that a verbal report must be used in lieu of physical documentation or directly witnessing the qualifying vitals, documentation of the verbal report will serve as the source documentation for determining eligibility. Verbal reports will be documented in the emergency medical record and will detail the information reported and by whom.

Study participants will be randomly assigned to either LTWB or standard of care based on a cluster randomized design. Patients will be randomly assigned by EMS base to receive either standard of care (one-month time interval) or LTWB (two-month time interval).

Subjects will undergo initial blood sampling for our secondary outcomes of interest during the first 60 minutes from arrival to the TOWAR trial site. A point of care rapid or conventional thromboelastography (TEG) will be performed for coagulation parameter measurements as close to arrival as possible and as close to 24 hours as possible (+/- 12 hours) when clinical care allows.

V. Potential Risks and Benefits

Potential Risks

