For the primary trial outcome, an indicator of death within 30 days will be generated for each participant. A two-sided z-test for proportions controlling for within cluster correlation utilizing the methods of Donner and Klar will serve as the primary approach to compare the proportions between the treatment arms.²⁴ A mixed-effects logistics regression model will be used to assess the independent impact of LTWB on 30-day survival after controlling for potential confounding effects of baseline characteristics which reveal imbalance between treatment groups. Random effects will be included for intercept, slope, service. Fixed effects will include treatment, baseline characteristics not balanced through random assignment, and month of study.

Analyses to test for the homogeneity of the treatment effect will be carried out for the pre-defined subgroups. Regression models appropriate for the outcome variable (e.g., mixed effect logistic regression for binary outcome variables) will be used to test for the homogeneity of the treatment effect. Main effects will be included in the model for treatment, the indicator of the subgroup and the two-way interaction between treatment and subgroup. If a statistically significant interaction is observed, we will reject the null hypothesis of a homogenous treatment effect.

AIM#2 Analysis: Determine whether prehospital old whole blood (age > 14 days) as compared to young whole blood (age ≤ 14 days) is associated with similar clinical outcomes, hemostasis, prevention of coagulopathy, and platelet function in patients at risk of hemorrhagic shock.

The analysis will begin by describing the baseline demographic and clinical characteristics of the overall population and then stratified by age of whole blood; whole blood age ≤ 14 days versus whole blood age > 14 days. For discrete variables, proportions will be generated, and a chi-square test will be used to test for differences between the proportions. For continuous characteristics, means (medians) and standard deviations (interquartile ranges) will be calculated and t-tests (Wilcoxon) will be used to compare the means (distributions) between treatment arms.

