Sample Size Justification and Power Analysis: The sample size calculations are based on the primary outcome, 30-day mortality, for Aim 1 of the study. With 40 service providers, a sample of 340 participants per treatment group is needed to detect a difference in the 30-day mortality rate of 26% vs. 16% (based on data from the PAMPer study), assuming 80% power, a type I error rate of 0.05, a two-sided alternative hypothesis, and an intraclass correlation coefficient of 0.02, as was observed in the PAMPer study.¹² The size of the ICC will have an impact on the size of the sample needed. If the ICC is smaller (e.g., 0.01 would require a sample size of 300 per arm), fewer people will be needed. However, if it is larger, more will be needed (e.g., 0.05 would require a sample size of 680 per arm).

Using a 2:1 random allocation of study participants to LTWB:standard of care, and enduring that there are 340 participants in the standard care arm, will lead to a total sample size of 1020, with 680 participants receiving LTWB. Assuming that 60% of these participants will receive whole blood \leq 14 days in age and 40% will receive whole blood $>$ 14 days in age, based on a chi-square test of proportions there will be 80% power to detect a higher mortality rate of 22.6% among those receiving whole blood over 14 days old, assuming a 30-day mortality rate of 14% among those receiving whole blood \leq 14 days, a type 1 error of 0.05 and a two-sided alternative hypothesis (that whole blood $>$ 14 days in age has a worse outcome than whole blood \leq 14 days) vs. the null hypothesis that whole blood $>$ 14 days is the same or better than whole blood \leq 14 days).

Randomization of Ineligible Subjects: It is anticipated that there will be a small proportion of patients enrolled who receive whole blood or standard care that in retrospect will not have met the entry criteria and are thus ineligible. In this circumstance, patients will be analyzed according to the group to which they were randomized. Subgroup analyses based on eligibility criteria will be performed if the number of patients so affected is large. However, based on the relatively

limited inclusion and exclusion criteria it is anticipated that the frequency of this event will be low.

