Missing Data: Consistent with the intention-to-treat principle, the analysis methods used to analyze the primary outcome include all patients according to their assigned intervention. Baseline characteristics of patients with missing outcome data will be compared. Missing primary outcome data will be imputed. Based on data from PAMPer, it is anticipated that the missing data rate will be less than 5%.¹²

Non-adherence: In some circumstances, patients may receive standard care instead of the whole blood intervention when randomized to whole blood. Non-adherence is most likely to occur in the case of the patient who requires urgent care in the prehospital environment where logistics do not allow the intervention to be administered. Fortunately, this event is relatively rare. In keeping with the intention-to-treat analytic design, these patients will be analyzed with the group to which they were randomized.

Interim Analyses: In concert with the DSMB, prior to initiation of the trial, the final monitoring plan will be developed to serve as the guide to the DSMB's decision-making process concerning early stopping of the trial. In making the decision to recommend termination of the study, the DSMB shall be guided by several types of information: (i) a formal stopping rule based on the primary analysis, (ii) information on safety outcomes by treatment group, (iii) consistency between results for primary and secondary outcomes, and (iv) consistency of treatment effects across subgroups.

We have designed this trial with two-interim looks before the final analysis. The groups sequential approach of Lan and DeMets using the O'Brien-Fleming spending function will be used to determine the type I error boundaries for each analysis. The selection of the Lan and DeMets approach permits flexibility with respect to the number of interim analyses. Two formal interim analyses of efficacy will be performed when 33% and 67% of the enrolled participants reach the assessment of the primary endpoint (30 days after injury). The level of significance will maintain an overall p value of 0.05 according to stopping boundaries leaving a p value of 0.038; two sided, for the final analysis with a final z-value of 1.993.

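### The per-arm sample sizes (300, 340, 680) fit a parallel trial of 20 services per arm, not this trial's 40 alternating services; the error is conservative, but Aim 1 power at the planned 680/340 should be restated.

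*Combined protocol and SAP*

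**What the plan says.** Under Sample Size Justification and Power Analysis (section VI) the plan states: "With 40 service providers, a sample of 340 participants per treatment group is needed to detect a difference in the 30-day mortality rate" of 26% versus 16%, with 80% power, two-sided 0.05 and an ICC of 0.02. It gives 300 per arm for an ICC of 0.01 and says that "0.05 would require a sample size of 680 per arm". The total then follows: "Using a 2:1 random allocation of study participants to LTWB:standard of care", with 340 in standard care, gives 680 + 340 = 1020. No Aim 1 power is given for 680/340. The paragraph mentions neither alternation nor a correlation between periods.

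Under Randomization and Masking (section II), "an EMS service/agency will be randomly assigned to one of three three-month repeated" sequences, each with two LTWB months and one standard-care month. Section IV gives the same one-month and two-month intervals, though it names the EMS base as the unit.

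The primary test (AIM#1 Analysis) is "A two-sided z-test for proportions controlling for within cluster correlation", by a cited textbook method. A separate covariate-adjusted logistic model follows, of which the plan says: "Random effects will be included for intercept, slope, service".

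**The concern.** Every service supplies patients to both arms, so much of what distinguishes one service from another cancels in the treatment comparison. A parallel cluster formula has no such cancellation, and it spreads each arm over half the services. If the sample size rests on that formula, the stated requirements and their dependence on the ICC describe a different trial. A monitoring board that saw an ICC near 0.05 would read from the plan that 340 standard-care patients is half of what is needed.

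The same question touches the test. Its standard error depends on whether the covariance between a service's LTWB and standard-care patients enters the variance, and the plan does not say. The formal stopping rule and the other binary outcomes use the same analysis.

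**Working it through.** **Inputs from the plan.** Mortality 26% (standard care) and 16% (LTWB); two-sided 0.05; 80% power; ICC 0.01, 0.02 and 0.05; 40 services; 340 standard-care and 680 LTWB patients.

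**Step 1: reproduce the stated figures.** Per arm without clustering:

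n0 = (1.96 + 0.8416)² × (0.26×0.74 + 0.16×0.84) / 0.10² = 256.5.

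With k services per arm and design effect 1 + (n/k − 1)×ICC, solving for n gives n = n0(1 − ICC) / (1 − n0×ICC/k). For k = 20 and ICC 0.02, 256.5×0.98 / (1 − 0.2565) = 338.1, which is 17 whole patients in each of 20 services, or 340.

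| ICC | Stated | k = 20, raw | k = 20, whole patients per service | k = 40, raw | k = 40, whole patients per service |
|---|---|---|---|---|---|
| 0.01 | 300 | 291.3 | 300 | 271.3 | 280 |
| 0.02 | 340 | 338.1 | 340 | 288.4 | 320 |
| 0.05 | 680 | 679.2 | 680 | 358.7 | 360 |

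All three match with 20 services per arm and none with 40. A pooled-variance n0 of 259.2 leads to the same reading: 294.9, 343.0 and 699.9 for k = 20; 274.4, 291.9 and 364.4 for k = 40. The k = 40 columns are for services in both arms with zero between-arm correlation. At ICC 0.05, 680/360 = 1.9.

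**Step 2: power of the planned 680/340.** Each of 40 equal services contributes 17 LTWB and 8.5 standard-care patients. Let r be the correlation between two patients of one service in different arms. The documents do not give r; I assume a range from 0 to the ICC.

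Variance = (0.16×0.84/680)(1 + 16×ICC) + (0.26×0.74/340)(1 + 7.5×ICC) − 2r√(0.1344×0.1924)/40.

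Power = Φ(0.10/SE − 1.96).

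- ICC 0.01: 93% (r = 0) to 95% (r = 0.01).
- ICC 0.02: SE 0.0302 to 0.0274; power 91.2% to 95.4%.
- ICC 0.05: SE 0.0337 to 0.0271; power 84.4% to 95.9%.

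Using a pooled null variance in the test gives 92.5–96.3% at ICC 0.02, about one point higher.

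**Step 3: final cut-off and allowances, ICC 0.02.** The Interim Analyses paragraph describes its boundaries as "leaving a p value of 0.038; two sided, for the final analysis with a final z-value of 1.993". The z for p = 0.038 is 2.075, so the two do not correspond; that is a separate matter. Power is 90.6–95.1% at 1.993 and 89.2–94.2% at 2.075. Now assume that 5% of LTWB patients get standard care (LTWB rate 0.95×16% + 0.05×26% = 16.5%) and that 5% of outcomes are missing (646/323). Power at 2.075 is then 84.0–90.2%.

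**Step 4: unequal services.** Service sizes are not in the documents. I assume a coefficient of variation of 1. Simulation of the three rotating sequences (40 services, 48 months, 1020 patients, leave-one-service-out standard error) gave 84–94% at ICC 0.02 and 68–93% at 0.05. The range falls below 80% only at ICC 0.05.

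**Step 5: what the covariance is worth in the test.** A test that drops the last variance term uses the r = 0 standard error whatever r is. At r = ICC that error is too large by 0.0302/0.0274 − 1 = 10% (ICC 0.02) or 0.0337/0.0271 − 1 = 24% (ICC 0.05); at r = 0 it is correct. At r = ICC, power at the planned effect is Φ((0.10 − 1.96×0.0302)/0.0274) = 93.2% instead of 95.4% at ICC 0.02, and 89.6% instead of 95.9% at 0.05.

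**The case against.** The split into 20 and 20 is nowhere in the plan. That is true, and it remains an inference, but three exact matches against none make it a firm one.

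The plan uses 340 as a floor for the smaller arm and obtains the other 340 LTWB patients from the 2:1 allocation, which also serves the blood-age comparison. Power above 80% follows from that conservative choice, and 680 at ICC 0.05 is a sensitivity figure rather than a planning input. This stands, and it is why no change in the number of patients follows. It does not make the stated figures right for this design.

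On the test, a reader might infer that the primary z-test ignores the pairing of arms within a service and so wastes power. The documents do not support that. The plan says that it controls for within-cluster correlation by a cited method whose text was not available here, and if the cluster is the service, such a control can already carry the between-arm covariance. The mixed model also includes service. At the planned effect and ICC 0.02 the loss would in any case be at most about 2 points. Larger losses need a higher ICC or a smaller effect than planned, together with a between-arm correlation close to the ICC. Ignoring a positive covariance makes the test conservative; it does not inflate type I error.

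The term EMS base is also a weak point of attack: the randomization section uses base and service almost interchangeably, and 40 services is the only cluster count given.

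**Conclusion.** The stated per-arm requirements are wrong for the design as described. They answer a 1:1 parallel question, and the figure for ICC 0.05 is nearly twice what 40 alternating services need even with no between-arm correlation. Power at 680/340 is about 91–95% at the planned ICC and 84–96% at 0.05. This assumes equal services, a between-arm correlation from 0 to the ICC and z 1.96; very unequal services lower it.

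A reader might take the 680 figure to mean that the trial is underpowered at ICC 0.05, or take the mismatch as a reason to change the total. Neither follows: the error is conservative and 1020 is not in doubt. The handling of a service's two arms in the primary test is an unstated detail to settle, not a demonstrated flaw.

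**What to change.** Keep 1020 patients. Replace the per-arm and ICC sentences with Aim 1 power at 680/340 for 40 alternating services, over a stated range of ICC, between-arm correlation and service-size variation, at the final cut-off.

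In the same amendment, made before outcomes are compared by arm, state that the variance in the primary z-test uses the service as the cluster and includes the covariance between a service's two arms. Align the EMS base wording with this.

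The choice of estimator belongs to the sponsor's statistician, with its small-sample and interim behaviour checked first. A leave-one-service-out standard error with a t reference, for example, should not be adopted unchecked. In simulation it had about 2–4 points less power than an independent-arms test when the between-arm correlation was 0. At the first look it rejected at 0.0003–0.0009 against a nominal 0.0002.

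The cost is a SAP amendment and a recomputed power paragraph, with no extra patients or data. Power becomes a range rather than one figure, and the test description becomes slightly longer.

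### The final-analysis criterion is printed in two forms that disagree: z = 1.993 is a two-sided p of 0.046, and 0.038 appears to be the alpha spent at the final look

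*Combined protocol and SAP*

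**What the plan says.** All the inputs are in the Statistical Analysis Plan (section VI), under Interim Analyses:

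- Number of looks: "We have designed this trial with two-interim looks before the final analysis".
- Method: "Lan and DeMets using the O'Brien-Fleming spending function will be used to determine the type I error boundaries for each analysis".
- Timing: "Two formal interim analyses of efficacy will be performed when 33% and 67% of the enrolled participants reach the assessment of the primary endpoint".
- Overall level: "The level of significance will maintain an overall p value of 0.05 according to stopping boundaries", followed directly by "leaving a p value of 0.038; two sided, for the final analysis with a final z-value of 1.993".

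The Sample Size Justification in the same section uses the same level: "a type I error rate of 0.05, a two-sided alternative hypothesis". The primary test, under the Aim 1 analysis, is a two-sided z-test for proportions adjusted for within-cluster correlation.

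The plan prints no interim boundaries and no nominal level of 0.046, and does not say how 0.038 was obtained. It refers to a monitoring plan to be agreed with the DSMB before the trial starts, which is not part of these documents.

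**The concern.** One success criterion for the primary outcome is given as a p value and as a z value, and the two do not convert into each other. A reader will compare the observed p with 0.038 or the observed z with 1.993. For any final result with |z| between 1.993 and 2.075 (two-sided p between 0.038 and 0.046) the answers differ. No other part of the documents says which figure governs, so the choice would be made after the result is known.

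The stake is a disputed conclusion on 30-day mortality or, if the p figure is followed, a test stricter than the one planned. A false-positive rate above 0.05 is not at stake.

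**Working it through.** **Step 1. Convert the printed figures.** This needs no assumption about the design.

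- Two-sided p for z = 1.993: 2 × [1 − Φ(1.993)] = 0.0463.
- z for a two-sided p of 0.038: Φ⁻¹(1 − 0.019) = 2.075.
- Reading 0.038 as one-sided does not rescue it: Φ⁻¹(1 − 0.038) = 1.774.

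**Step 2. Reproduce the plan's boundary.** Inputs from Interim Analyses: overall two-sided alpha 0.05, O'Brien-Fleming-type spending, looks at 33%, 67% and 100%. With 0.025 spent per side, the cumulative two-sided alpha at information fraction t is

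α(t) = 4 × [1 − Φ(z₀/√t)], where z₀ = Φ⁻¹(1 − 0.05/4) = 2.2414.

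Boundaries were then found by recursive numerical integration. For looks at 1/3, 2/3 and 1:

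| Look | Cumulative alpha | Alpha spent at this look | Boundary z | Nominal two-sided p |
|---|---|---|---|---|
| 1/3 | 0.0002 | 0.0002 | 3.710 | 0.0002 |
| 2/3 | 0.0121 | 0.0119 | 2.511 | 0.0120 |
| 1 | 0.0500 | 0.0379 | 1.993 | 0.0463 |

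The final boundary reproduces the printed 1.993. The final-look increment, 0.0500 − 0.0121 = 0.0379, rounds to the printed 0.038. With looks at exactly 0.33 and 0.67 the final row is z = 1.994, p = 0.0462, increment 0.0377, which rounds to the same 0.038.

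**Step 3. Try other designs.** None pairs p = 0.038 with z = 1.993:

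- O'Brien-Fleming-type spending applied directly to 0.05: final z 2.015 to 2.016, p 0.044, increment 0.033 to 0.034.
- Classical O'Brien-Fleming: z 2.004, p 0.045.
- Pocock-type spending: z about 2.30, p about 0.022.

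**Step 4. What follows if p <= 0.038 is applied at the end.** Keep the interim boundaries and set the final cut-off to 2.075.

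- Alpha spent at the final look is 0.0302, so overall alpha is 0.0002 + 0.0119 + 0.0302 = 0.0423 instead of 0.0500.
- Power over all looks, assuming 80% fixed-sample power (drift 1.960 + 0.842 = 2.802): 77.2% instead of 79.5%.

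**Step 5. The same with the trial's own figures.** From the Sample Size Justification: 26% versus 16%, 340 standard care and 680 whole blood, 40 services. Mean cluster size is 1020/40 = 25.5. I assume a design effect of 1 + 24.5 × ICC and an unpooled standard error.

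| ICC | Design effect | Power, z 1.993 | Power, z 2.075 | Loss (points) |
|---|---|---|---|---|
| 0 (no inflation) | 1.000 | 94.9% | 94.1% | 0.9 |
| 0.01 | 1.245 | 89.7% | 88.2% | 1.5 |
| 0.02 | 1.490 | 83.8% | 81.8% | 2.0 |
| 0.05 | 2.225 | 67.4% | 64.5% | 2.8 |

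Losses are computed before rounding. At ICC 0.02 the pooled rate is (680 × 0.16 + 340 × 0.26)/1020 = 19.3%. The observed difference needed at the final look is then 6.4 points with z = 1.993 and 6.6 points with z = 2.075.

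**Step 6. Sensitivity to timing.** Looks at 30% and 60% give final z 1.981 (p 0.048, increment 0.042). Looks at 40% and 80% give 2.026 (p 0.043, increment 0.026).

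**The case against.** The best defence is that the operative rule is sound. The plan says the spending function sets the boundary at each analysis, and an analyst who follows it arrives at about 1.993; the printed figures only illustrate the rule. The verb *leaving* also suggests the authors meant remaining alpha, so the fault may be a single wrong noun. The monitoring plan agreed with the DSMB may hold the correct boundaries. All of this is fair, but none of it removes the contradiction: the text calls 0.038 a two-sided p value for the final analysis, and remaining alpha is not a threshold for an observed p.

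Three further points stand in part:

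- **Origin.** That 0.038 is the alpha increment is an inference, since the plan does not give its source. It is a strong inference, because one calculation from the plan's own inputs returns both printed numbers. The mismatch does not depend on it.
- **Power figures.** The design effect treats each service as staying in one arm, whereas Randomization and Masking has services alternating between arms. It therefore probably overstates the variance. The row with no inflation shows the loss could be as small as 0.9 points.
- **Likelihood.** The chance of ending in the disputed band without stopping earlier is small: 0.0379 − 0.0302 = 0.8% under the null, and 79.5% − 77.2% = 2.3% at the drift for 80% power.

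**Conclusion.** The point holds. The two printed forms of the final criterion contradict each other. Under the plan's own inputs the final boundary is z = 1.993, a nominal two-sided p of 0.046, and 0.038 is best explained as the alpha spent at the final look.

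The practical effect is modest. Neither reading inflates type I error. Using 0.038 as a p cut-off leaves about 0.008 of the planned 0.05 unspent and costs about 2 points of power, with a range of 0.9 to 2.8 points over the assumptions tried. It still deserves correction, because it concerns the decision rule for the primary outcome and the text leaves two answers available for a borderline result.

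**What to change.** Replace the end of the sentence with wording such as: *the final analysis will use |z| >= 1.993 (nominal two-sided p of about 0.046); the alpha spent at the final look is 0.038.*

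Then add: *planned boundaries are z of about 3.71, 2.51 and 1.99; they will be recalculated from the spending function at the actual information fractions.* The spending rule already implies this second sentence. Stating it stops 1.993 from being applied as a fixed number if the looks fall away from 33% and 67%. If the DSMB monitoring plan quotes either figure, it should be brought into line.

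The cost is two sentences in the analysis plan, settled before the final analysis. Design, sample size and enrolment do not change.
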